## **Protocol Synopsis**

Study title	Alcohol Labeling Study
Funder	National Institute on Alcohol Abuse and Alcoholism
Study rationale	

• Policymakers and public health organizations are increasingly interested in communicating alcohol's harms to the public, including through mandated warning labels.

• Communicating alcohol's harms through front-of-package alcohol health warnings could reduce alcohol consumption and alcohol-related health harms.

• Few studies have experimentally evaluated whether front-of-package alcohol warnings change drinking behavior.

Study objectives	
Primary
 

• Evaluate whether front-of-package alcohol health warnings reduce the number of alcoholic drinks consumed per day.

 
Secondary
 

• Evaluate whether front-of-package alcohol health warnings affect other alcohol-related behaviors and inform consumers.

Study design	Randomized clinical trial
Number of participants	~720 participants.
Study duration	Each participant is in the trial for ~3 weeks. The trial enrollment period is expected to last ~24 months.
Study phases	The trial will have two phases: (1) Screening : screening for eligibility and obtaining consent and (2) Intervention : intervention/experimental treatment

## **Study protocol**

Participants will be invited to attend 3 in-person visits, spaced ~1 week apart. Participants will be instructed to bring 8 days' worth of unopened alcohol containers to each trial visit. Study staff will randomize participants to 1 of 2 trial arms (front-of-package health warnings or control labels) at the first visit. At each visit, staff will apply labels per participants' assigned arm to the front of all alcohol containers. Participants will take a computer survey at each visit. Participants will take a final survey remotely approximately 1 week after the final in-person visit. Participants will answer two questions by text message each day they are in the study.

## **Statistical analysis plan**

### **General principles**

Analyses will be intent-to-treat, including all participants randomized at Visit 1, except when noted. We will use a critical alpha of 0.05 or 95% confidence intervals, and two-tailed tests to conduct all statistical tests.

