### **Predictions**

We predict that front-of-package alcohol health warnings will lead to fewer drinks consumed per day (primary outcome), compared to the control. In terms of secondary outcomes, we predict that compared to the control, front-of-package alcohol health warnings will lead to

greater intentions to limit drinking, forgoing a drink, perceived control over drinking, learning something new, knowledge of harms from alcohol in warnings, reminding of harms of alcohol, and perceived likelihood of harms from alcohol. We predict that, compared to the control, front-of-package alcohol health warnings will lead to lower maximum number of drinks consumed in a day, proportion of days drinking during the study, and perceived healthfulness of alcohol.

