### **Statistical methods**

We will descriptively present demographic characteristics separately for each trial arm but will not test for balance, following CONSORT guidelines. Assuming sufficient internal consistency (Cronbach's alpha $\geq$ 0.70), we will average responses to all measures with 3 or more items.

All analyses will be intent-to-treat, except where noted. To examine the impact of trial arm on the primary outcome, we will run a mixed effects linear regression model to account for repeated measures across participants. This model will regress number of drinks consumed per day on indicators for trial day when drinking was reported (within subjects, level 1 variable, fixed effect), whether the trial day when drinking was reported was a weekend versus weekday (within subjects, level 1 variable, fixed effect), and trial arm (between subjects, level 2 variable, fixed effect). Analysis will treat the intercept as random. In "per protocol" sensitivity analyses, we will re-run the primary outcome model among those with high adherence to the labeling protocol.

We will explore whether the impact of trial arm on the primary outcome differs by the following participant characteristics: baseline alcohol use, baseline intentions to limit drinking, gender, age, and education. Using the same modeling approach as for the primary outcome and separate models for each moderator, we will regress number of drinks consumed per day on trial arm, the moderator, and interactions between trial arm and the moderator. We will report the statistical significance of the interaction terms. We will estimate the impact of trial arm on the outcome at each level of the moderator, adjusting for these post-hoc tests using a Bonferroni-Holm correction.

Next, we will examine the impact of trial arm on secondary outcomes. We will use mixed effects linear and logistic models for outcomes with repeated measures. The predictor will be trial arm (between subjects, level 2 variable, fixed effect); analyses will treat the intercept as random. We will use standard logistic and linear models for outcomes measured only once, with trial arm as the only predictor.

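### Do ten secondary predictions, each tested at two-sided 0.05, need a multiplicity correction?

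*Combined protocol and SAP*

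**What the plan says.** The General principles section of the SAP sets one significance rule for the whole trial: "We will use a critical alpha of 0.05 or 95% confidence intervals, and two-tailed tests to conduct all statistical tests".

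The Predictions section then separates two tiers. The primary prediction is "fewer drinks consumed per day (primary outcome), compared to the control". The secondary predictions of an increase are "greater intentions to limit drinking, forgoing a drink, perceived control over drinking, learning something new, knowledge of harms from alcohol in warnings, reminding of harms" (six outcomes), "and perceived likelihood of harms from alcohol" (a seventh). The predictions of a decrease are "lower maximum number of drinks consumed in a day, proportion of days drinking during the study, and perceived healthfulness of alcohol" (three more), which makes ten.

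Statistical methods introduces the analysis of these ten with "Next, we will examine the impact of trial arm on secondary outcomes". It gives one arm effect per outcome and no ordering, gatekeeping or adjustment. The plan's only correction sits in the moderator analysis of the primary outcome, which opens with "We will explore whether the impact of trial arm on the primary outcome differs by the following participant characteristics". There, arm effects are estimated at each level of a moderator, "adjusting for these post-hoc tests using a Bonferroni-Holm correction".

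**The concern.** Error control appears to be in the wrong place. The exploratory subgroup contrasts are corrected, while ten outcomes with directions stated in advance, which serve the secondary objective in the Synopsis, are not. The interaction tests for the five moderators are not corrected either.

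The trial is meant to inform policy on mandated warning labels. If the primary result were null and one or two secondary outcomes reached p < 0.05, those could be presented as predictions borne out. The plan states no limit on the chance that such results are noise, and it does not say whether a significant secondary result confirms a prediction or only supports it.

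**Working it through.** **Inputs from the documents.** Two-sided alpha 0.05 for every test (General principles); ten secondary outcomes (Predictions); 720 participants in two equal arms, 21 daily measures, intraclass correlation 0.60 and 15% missingness per daily measure (Sample size needs). The documents give no correlation between outcomes, so a range is assumed.

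**1. The plan's own power figure.** With 21 × 0.85 = 17.85 observed days per person, the SD of a person mean in total-SD units is √(0.60 + 0.40/17.85) = 0.789. The standard error of the arm difference is 0.789 × √(4/720) = 0.0588.
- d = 0.17: 0.17/0.0588 = 2.89, power 82.4%.
- d = 0.18: 0.18/0.0588 = 3.06, power 86.5%.

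These agree with the stated values of over 80% and over 85%. They concern the primary test alone, which is unaffected by how the secondaries are handled.

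**2. At least one false positive among ten true nulls, either direction.** Under independence, 1 - 0.95^10 = 40.1%. For jointly normal two-sided statistics, Šidák's inequality makes this the maximum under any correlation.

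**3. At least one false positive in the predicted direction.** This is the event the concern fears. Each test then contributes 0.025, and under independence 1 - 0.975^10 = 22.4%. That is the ceiling if the statistics, signed towards their predictions, are not negatively correlated.

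Simulation with 400,000 draws and a common correlation gives:

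| Assumed correlation | Either direction | Predicted direction | Either direction, smallest p against 0.005 |
|---|---|---|---|
| 0.2 | 37.6% | 19.5% | 4.8% |
| 0.3 | 35.3% | 17.9% | 4.6% |
| 0.5 | 28.7% | 14.3% | 3.8% |
| 0.7 | 21.3% | 10.7% | 2.9% |
| 0.9 | 12.6% | 6.3% | 1.6% |

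**4. Interaction tests.** One test for each of five moderators would give 1 - 0.95^5 = 22.6% under independence. The plan does not fix the count at five: Statistical methods speaks of interaction terms in the plural and of moderator levels, so a moderator with several categories could have more than one term. The 22.6% is an illustration.

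**5. What Holm across ten would cost.** The strictest step is 0.05/10 = 0.005. For a continuous outcome measured once with complete data, the effect detectable with 80% power is (z + 0.8416) × √(4/720):
- alpha 0.05: (1.960 + 0.8416) × 0.0745 = 0.209.
- alpha 0.005: (2.807 + 0.8416) × 0.0745 = 0.272.

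Matching the smaller effect at the stricter level would take (3.649/2.802)² = 1.70 times the participants. At d = 0.209 the expected statistic is 0.209/0.0745 = 2.80, almost exactly the critical value of 2.807, so power falls from 80% to about 50%. If 15% of these outcomes were missing (an assumption, since the plan gives that rate only for diary days), n = 612 and the two detectable effects become 0.226 and 0.295. Later Holm steps are less strict, so this is the worst case. For outcomes analysed by logistic regression, d does not apply directly.

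**The case for a change.** The strongest case for a change is that the plan accepts the need for Holm in one place and gives no reason for omitting it in another. A rule fixed in advance is more credible than one chosen after the results, and it would take one sentence. Even if the knowledge and reminder outcomes are truly affected, three drinking-behaviour secondaries remain (forgoing a drink, maximum drinks, proportion of days drinking). These alone carry a two-sided false-positive chance of 1 - 0.95^3 = 14.3% under independence and about 12% at correlation 0.5. They are the outcomes a reader would turn to after a null primary.

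The arithmetic stands, and so does the observation that the plan is silent on how secondary results should be read. The charge of inconsistency is weaker. Level-specific contrasts all put the same question to the same outcome in different subgroups, where picking out the best-looking subgroup is the main hazard, so a local correction makes sense there. The ten secondary outcomes ask different questions. Because all ten and their directions are listed beforehand, a reader can see one success in ten for what it is. Asking for further correction of interaction tests in an analysis already labelled exploratory is a matter of preference.

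**Conclusion.** No change to the plan is needed. The facts are as described: ten secondary predictions, 0.05 for each, and Holm confined to moderator contrasts. But the plan designates a single primary outcome, never calls the secondaries confirmatory, and makes no family-wise claim that the analysis would break.

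The 40.1% requires all ten nulls to be true, independent tests, and the counting of results that contradict the prediction. For a falsely supported prediction the figure is about 22% under independence and 14% to 19% at assumed correlations of 0.5 to 0.2. The realistic figure is likely lower still. Several outcomes overlap (maximum drinks with drinking days, perceived harm with perceived healthfulness), and learning, knowledge and reminding lie close to the content of the warnings, so a global null is a worst case.

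Against that, Holm would lower the family-wise rate to at most 5% but raise the detectable effect from 0.21 to 0.27 at the strictest step. Experienced statisticians choose differently here, and leaving labelled secondaries unadjusted is defensible. The missing statement of their status is a detail that analysts would sensibly fill when reporting, by showing all ten estimates with 95% confidence intervals and describing them as unadjusted and supportive. This conclusion would not hold if the trial's success were claimed on a secondary outcome, which nothing in the plan proposes.

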### **Predictions**

We predict that front-of-package alcohol health warnings will lead to fewer drinks consumed per day (primary outcome), compared to the control. In terms of secondary outcomes, we predict that compared to the control, front-of-package alcohol health warnings will lead to

greater intentions to limit drinking, forgoing a drink, perceived control over drinking, learning something new, knowledge of harms from alcohol in warnings, reminding of harms of alcohol, and perceived likelihood of harms from alcohol. We predict that, compared to the control, front-of-package alcohol health warnings will lead to lower maximum number of drinks consumed in a day, proportion of days drinking during the study, and perceived healthfulness of alcohol.

### **Statistical methods**

We will descriptively present demographic characteristics separately for each trial arm but will not test for balance, following CONSORT guidelines. Assuming sufficient internal consistency (Cronbach's alpha $\geq$ 0.70), we will average responses to all measures with 3 or more items.

All analyses will be intent-to-treat, except where noted. To examine the impact of trial arm on the primary outcome, we will run a mixed effects linear regression model to account for repeated measures across participants. This model will regress number of drinks consumed per day on indicators for trial day when drinking was reported (within subjects, level 1 variable, fixed effect), whether the trial day when drinking was reported was a weekend versus weekday (within subjects, level 1 variable, fixed effect), and trial arm (between subjects, level 2 variable, fixed effect). Analysis will treat the intercept as random. In "per protocol" sensitivity analyses, we will re-run the primary outcome model among those with high adherence to the labeling protocol.

We will explore whether the impact of trial arm on the primary outcome differs by the following participant characteristics: baseline alcohol use, baseline intentions to limit drinking, gender, age, and education. Using the same modeling approach as for the primary outcome and separate models for each moderator, we will regress number of drinks consumed per day on trial arm, the moderator, and interactions between trial arm and the moderator. We will report the statistical significance of the interaction terms. We will estimate the impact of trial arm on the outcome at each level of the moderator, adjusting for these post-hoc tests using a Bonferroni-Holm correction.

Next, we will examine the impact of trial arm on secondary outcomes. We will use mixed effects linear and logistic models for outcomes with repeated measures. The predictor will be trial arm (between subjects, level 2 variable, fixed effect); analyses will treat the intercept as random. We will use standard logistic and linear models for outcomes measured only once, with trial arm as the only predictor.

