### **Sample size needs**

To estimate sample size needs, we assumed 21 repeated daily diary measures, 2 trial arms of equal size, an intraclass correlation of .60, and 15% missingness for any given daily diary measure. Power analyses used mixed effects linear regression, with 1,000 simulations. A sample size of 720 people would provide >85% power to detect effect sizes of  $d=.18$  or larger and >80% power to detect effect sizes of  $d=.17$  or larger. These effect sizes are conservative estimates as prior studies of non-alcoholic beverages indicate effect sizes of sugary drink health warnings on behavior of  $d=.25^1$  and  $d=.41^2$ .

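### The primary model leaves out baseline alcohol use, which the trial already plans to use as a moderator; pre-specifying it as a covariate would gain precision at almost no cost

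*Combined protocol and SAP*

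**What the plan says.** The Statistical methods section gives the primary model in full. "This model will regress number of drinks consumed per day on indicators for trial day when drinking was reported"; the other fixed effects are weekend versus weekday and trial arm. On the random part it says: "Analysis will treat the intercept as random". No participant-level covariate other than arm is included.

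The same section lists the exploratory moderators: "baseline alcohol use, baseline intentions to limit drinking, gender, age, and education". Each has its own model: "we will regress number of drinks consumed per day on trial arm, the moderator, and interactions between trial arm and the moderator". The results are then reported within subgroups: "We will estimate the impact of trial arm on the outcome at each level of the moderator". The form of the baseline alcohol variable (continuous or grouped) and the instrument are not stated.

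Under Sample size needs, the power simulation assumes 21 daily diaries, two equal arms, "an intraclass correlation of .60, and 15% missingness for any given daily diary measure". No covariate is mentioned. The stated result begins "A sample size of 720 people would provide >85% power to detect effect sizes of" d=.18, with more than 80% at d=.17.

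No section gives a reason for leaving baseline use out of the primary model.

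**The concern.** The two covariates in the primary model, trial day and weekend, vary within a person. They can reduce day-to-day noise, but the arm effect is a comparison between people. With an intraclass correlation of .60 and about 18 observed days each, its precision is governed almost entirely by how much people differ in their usual drinking. A baseline measure of drinking is an obvious candidate to explain some of that difference, and the trial already plans to have it.

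The moderator models do not fill the gap. They are exploratory, they contain the arm-by-moderator interaction, and they do not supply the primary estimate.

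What is at stake is the width of the primary confidence interval, and power if the true effect is at or below the planned d of .17 to .18. Validity is not in question. In a linear model, adjustment for a baseline covariate targets the same mean difference between arms.

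**Working it through.** **Inputs from the plan.** N = 720 in two equal arms; 21 diaries; 15% of diary entries missing; ICC .60; two-sided alpha .05; d of .17 and .18, read in units of the total daily SD.

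**Input not in the plan.** r, the correlation of baseline alcohol use with a participant's diary mean. It is assumed over a range.

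**Step 1: reproduce the stated power, unadjusted.**

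- Observed days per person: 21 × .85 = 17.85.
- Variance of a diary mean: v = .60 + .40/17.85 = .622.
- SE of the arm effect: sqrt(4 × .622/720) = .0588.
- Power = Φ(d/SE − 1.96), giving 82.4% at d=.17 and 86.5% at d=.18.

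These agree with the stated figures of more than 80% and more than 85%.

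**Step 2: where the variance lies.** Between-person share: .60/.622 = 96%. This is the ceiling for all person-level covariates together, not the share that baseline drinking alone would recover.

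**Step 3: adjust.** A covariate with correlation r removes about r² of the variance:

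- SE = sqrt(4v(1 − r²)/720)
- narrowing of the confidence interval = 1 − sqrt(1 − r²)
- effect detectable with 80% power = (1.96 + .8416) × SE
- unadjusted sample of equal precision = 720/(1 − r²)

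| r | SE | CI narrower by | Power, d=.17 | Power, d=.18 | Detectable d (80%) | Equivalent unadjusted N |
|---|---|---|---|---|---|---|
| 0 | .0588 | 0 | 82.4% | 86.5% | .165 | 720 |
| .1 | .0585 | 0.5% | 82.8% | 86.8% | .164 | 727 |
| .2 | .0576 | 2.0% | 83.9% | 87.8% | .161 | 750 |
| .3 | .0561 | 4.6% | 85.8% | 89.4% | .157 | 791 |
| .4 | .0539 | 8.3% | 88.4% | 91.6% | .151 | 857 |
| .5 | .0509 | 13.4% | 91.6% | 94.2% | .143 | 960 |
| .6 | .0470 | 20.0% | 95.1% | 96.9% | .132 | 1,125 |
| .7 | .0420 | 28.6% | 98.2% | 99.0% | .118 | 1,412 |

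**Step 4: effects outside the planned range.** At d=.15, power is 72.3% unadjusted, 76.2% at r=.3 and 83.8% at r=.5. At d=.25, unadjusted power is already Φ(.25/.0588 − 1.96) = 98.9%, so almost nothing is left to gain in power.

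**Step 5: grouped baseline.** If baseline use is entered as tertiles (normality assumed), about 79% of the variance reduction is kept. Power at d=.17 is then 85.1% (r=.3), 89.8% (r=.5) or 95.9% (r=.7). A median split keeps 64% and quartiles keep 86%.

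**Step 6: simulation check.** In 4,000 simulated trials per cell, with 720 people and randomly missing diaries, adjusted power at d=.17 was 86.1%, 88.6%, 91.6%, 95.0% and 98.0% for r = .3 to .7 in steps of .1. A separate simulation, with the covariate expressed as a share of between-person variance, gave type I error of 4.7% with and without adjustment. Both simulations used person means, normal errors and known variance components. They confirm the formula but do not test skewed daily counts.

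**The case against.** The strongest reply is that nothing here is wrong. The primary model is fully specified, it matches the model behind the power calculation, and an unadjusted randomized comparison is a legitimate choice. That stands, and it is why the point is an optional improvement.

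Second, the size of the gain does not come from the documents. If screening restricts the range of drinking, or the instrument is crude, r could be low; at r=.1 or .2 the gain is trivial. That also stands. But a small r only shrinks the benefit. It creates no appreciable downside, since one degree of freedom among 720 people is negligible.

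Third, the plan regards d=.17 to .18 as conservative beside the d=.25 and d=.41 it cites from earlier studies. At those effects power is close to its maximum without adjustment. That is correct for power, although a narrower confidence interval would remain useful for the estimate itself.

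Fourth, adjustment is not entirely free. It needs a named instrument, a functional form, a missing-data rule and confirmation that the measure precedes randomization. The Study protocol section places both randomization and a computer survey at the first visit without giving their order. The word baseline implies that the measure comes first, but the plan should say so. These are a few words of specification, and they do not alter the conclusion.

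**Conclusion.** The point holds as an optional efficiency improvement. The primary model omits a participant-level covariate that the trial already plans to use, while about 96% of the variance governing the arm comparison is between people. The planned analysis is valid and reaches its stated power without the change.

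For assumed r between .3 and .7, adjustment narrows the primary confidence interval by 4.6% to 28.6% and lowers the effect detectable with 80% power from .165 to between .157 and .118. These figures rest on the plan's ICC, diary count and missingness, on a linear relation between baseline use and the diary mean, and on an r that the documents do not supply. The direction of the result is secure; its size is not.

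**What to change.** In the Statistical methods section:

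- Add baseline alcohol use to the primary model as a level-2 fixed effect, as a continuous term if it is measured that way and otherwise in the form collected. The per-protocol analysis re-runs the primary model and should carry the same term.
- Name the baseline measure and state that it is taken before randomization.
- Use simple imputation, pooled over arms, for any missing baseline values, so that the analysis set in the General principles section is preserved: "Analyses will be intent-to-treat, including all participants randomized at Visit 1, except when noted".
- Keep the unadjusted model as a sensitivity analysis.
- Make the change before outcome data are seen by arm, so that it cannot appear data-driven.

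The cost is a few SAP sentences and one degree of freedom (or the number of categories minus one). No new data are needed, because the moderator analysis already requires the variable.

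### The per-protocol model compares a subset formed after randomization and leaves out baseline drinking; add that covariate, and show the intent-to-treat model with the same covariate beside it

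*Combined protocol and SAP*

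**What the plan says.** The SAP section General principles sets the main analysis set: "Analyses will be intent-to-treat, including all participants randomized at Visit 1, except when noted".

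Under Statistical methods, the primary model is a mixed linear regression of daily drinks on trial day, weekend versus weekday and arm, with a random intercept. Arm is its only between-person term. The sensitivity analysis changes only the analysis set: "we will re-run the primary outcome model among those with high adherence to the labeling protocol".

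Baseline drinking appears in the same section, but only in separate exploratory moderator models, among "the following participant characteristics: baseline alcohol use, baseline intentions to limit drinking, gender, age, and education". Those models include an interaction with arm and are not described for the adherent subset.

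The Study protocol section puts randomization at the first of three visits. Participants are to bring eight days' "worth of unopened alcohol containers to each trial visit", and "At each visit, staff will apply labels" according to assigned arm. How far a participant's alcohol was labeled over the study is therefore settled after randomization.

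**The concern.** Randomization makes the arms comparable among everyone randomized, but not within a subset chosen on later behavior. Here that behavior is returning with unopened alcohol to be labeled, which could plausibly be related to how much a person drinks. After Visit 1 the arms also live with different labels, so retention in the subset could differ between them.

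Bias needs two things together: being kept must be related to drinking, and either the share kept or the strength of that relation must differ by arm. If one is absent there is no bias.

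This is the only sensitivity analysis of the primary outcome that the documents name. If it disagrees with the intent-to-treat result, the planned model makes no allowance for who was kept, although a relevant baseline measure is to hand.

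**Working it through.** **Inputs from the documents.** 720 participants in two equal arms (360 each), 21 daily measures, "an intraclass correlation of .60, and 15% missingness for any given daily diary measure" (Sample size needs), and "We will use a critical alpha of 0.05 or 95% confidence intervals, and two-tailed tests" (General principles).

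**Assumed inputs, not in the documents.** Share kept 70% to 85%; log-odds slope g of being kept per SD of a person's underlying drinking tendency u, 0 to ±.5; correlation rho of baseline drinking with u, .5 to .8.

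**1. The plan's own figure.** Observed days per person: 21 × .85 = 17.85. Variance of a person mean, in total-SD units: .6 + .4/17.85 = .6224. Intent-to-treat SE = √(2 × .6224/360) = .0588. Power at d = .17: Φ(.17/.0588 − 1.96) = 82.4%. At d = .18: 86.5%. Both agree with the stated >80% and >85%, so this variance model is used below. It approximates the random-intercept contrast by person means.

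**2. Bias in the subset with no true effect, being kept logistic in u.** Bias = √.6 × (mean of u among those kept, warnings arm, minus the same in the control arm). Worked case: slopes −.5 in both arms, 70% of control and 85% of warnings kept. The means of u are −.1427 (control) and −.0726 (warnings), so bias = .7746 × .0701 = .054.

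| Slopes, control / warnings | Kept, control / warnings | Bias (SD) | False positives |
|---|---|---|---|
| 0 / 0 | 70% / 85% | 0 | 5% |
| −.3 / −.3 | 75% / 75% | 0 | 5% |
| −.3 / −.4 | 75% / 75% | −.018 | 6% |
| −.3 / −.3 | 70% / 85% | +.034 | 8% |
| −.5 / −.5 | 70% / 85% | +.054 | 13% |
| 0 / −.3 | 75% / 75% | −.057 | 13% |
| 0 / −.5 | 75% / 75% | −.093 | 28% |

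The sign depends on the pattern: slopes 0 / +.5 give about +.09, and swapping the arms in the 70%/85% row with slopes −.5 gives −.054. The largest figure is .093/.17 = 55% of the planned effect.

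**3. What the covariate does to bias.** It depends on why people are kept.
- Kept according to u, with baseline an imperfect measure of u (the +.054 row): bias falls to about .041, .029 and .020 at rho .5, .7 and .8.
- Kept according to baseline drinking itself (slope −.5, warnings arm only, 75% kept, rho .5): about −.046 falls to about 0.
- Kept according to u (slope −.5) and baseline (slope +.5) in opposite directions, warnings arm only: bias grows, from about −.045 to −.069 at rho .5.

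**4. What the covariate does to precision, with no selection.** At 75% kept there are 270 per arm. Unadjusted SE = √(2 × .6224/270) = .068. Adjusted SE = √(2 × [.6(1 − rho²) + .0224]/270):
- rho .5: √(2 × .4724/270) = .059
- rho .7: √(2 × .3284/270) = .049
- rho .8: √(2 × .2384/270) = .042

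**5. Why the comparator needs the same covariate.** Take the SD of (per-protocol minus intent-to-treat) when there is no true gap, 75% kept.
- Neither adjusted: √(.0679² − .0588²) = .034.
- Only the subset model adjusted: √(SE²adj,subset + .0588² − 2 × .75 × SE²adj,subset) = .041, .047 and .051 at rho .5, .7 and .8.
- Both adjusted: √(SE²adj,subset − SE²adj,all) = .030, .025 and .021.

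Adjusting one model alone makes the comparison noisier; adjusting both makes it sharper.

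**The case against.** The strongest reply is that little turns on this analysis. Intent-to-treat is primary, the subset result is already called a sensitivity analysis, and re-running an identical model in a subset is a common convention that isolates the change in analysis set. Both arms have the same visits and staff-applied labels, so selection may well be the same in each. All of this stands, and it is why the severity is low. It does not remove the case for the covariate, which improves precision even when there is no selection. The matched comparator restores the like-for-like comparison that the convention offers.

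A reader might infer that adjustment reduces the bias without removing it, and want the SAP to say so. That is not generally true: depending on what drives adherence, the covariate can remove the bias, shrink it or enlarge it. The enlarging case needs opposing selection and is not claimed to be likely, but the SAP should not announce the result in advance.

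It is also fair to say that high adherence is undefined, and that the form of the baseline measure is not given. The moderator text says "We will estimate the impact of trial arm on the outcome at each level of the moderator", which may mean categories. Under selection on u alone, a continuous covariate removes about 25% to 64% of the bias and a median split about 16% to 41%. These are details to settle alongside the change, not the ground for it.

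**Conclusion.** The point holds as a free improvement, at the lowest severity. The per-protocol subset is formed after randomization, its model has no between-person term except arm, and a relevant baseline measure goes unused there.

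The precision gain rests on the assumed correlation of .5 to .8 and 75% kept. The bias range of 0 to about .09 SD rests wholly on assumed selection. A reader might take that range, or the 13% to 28% false-positive rates, as evidence that the planned analysis is biased. The documents do not support that: they give no adherence share and no relation between adherence and drinking, and the 28% figure needs selection in one arm only. Nor do they support any doubt about the primary result, which keeps everyone randomized.

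**What to change.** In Statistical methods:
- Add baseline alcohol use as a covariate in the per-protocol model, as a continuous measure if one is available.
- Report beside it the intent-to-treat model with the same covariate, labeled as a comparator only. The planned unadjusted intent-to-treat model stays primary.
- State that adjustment is expected to improve precision and may reduce selection bias explained by baseline drinking, but is not guaranteed to reduce or remove it, and that the per-protocol result is supportive only.

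Useful accompanying details: fix the adherence cut-off before outcomes are seen by arm, and report the share kept in each arm.

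Cost: a few lines of SAP wording, one extra model and a rule for missing baseline values. No new data are needed, and the primary analysis does not change.
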